Bintrafusp alfa administration		X	X	X	X	X	X	X	Q2W				Bintrafusp alfa is administered as a 1200 mg IV infusion over 1 hour (-10 minutes/+20 minutes; ie, over 50 to 80 minutes) Q2W for up to 2 years (or up to 2 years from confirmed CR). See Section 6.1 for information.	

	Screening	Intervention (treatment) Period								Safety Follow-up		Long Term Follow-up	Notes	
Assessment and Procedures	45 Day- to first dose	V1	V2	V3	V4	V5	V6	V7	Until PD	EOT	28 Days (±5 Days) After Last Treatment	12 Weeks (± 2 Weeks) After Last Treatment	Every 12 Weeks (± 2 Weeks)	D1: All assessments must be performed on day indicated (unless noted in assessment "Notes"). Day 15 through PD: Visits can be performed ±3 days. EOT: On day of or within 7 days of decision to discontinue. Follow up: Visits can be performed ±2 Weeks.
		W1	W3	W5	W7	W9	W11	W13						
		D1	D15	D29	D43	D57	D71	D85						
Response Assessments														
Tumor evaluation/staging (CT Scan/MRI/ other established methods)	X					X			Q8W up to 6 months., then Q12W	X	X		CT scan with contrast of the chest, abdomen, and pelvis is required. Screening scans for lesion assessments are required within 28 days of first dose. See Section 8.3 for additional information Q8W for the first 6 months (mos.) and Q12W thereafter, and at the final study visit. Schedule should not be affected by dose interruptions/delays. Confirmation of CR and/or PR should be performed at the next scheduled assessment but no sooner than 4 weeks. Before stopping the treatment, progressive disease should be confirmed by imaging at least 4 weeks after progression. See Section 7.1.1. If discontinued intervention without documented progression, then continue imaging Q8W for the first 6 months followed by Q12W until documented PD, or the start of any new anti-cancer therapy. A bone scan should be done as clinically indicated at screening and beyond. TA brain CT/MRI scan should be performed as clinically indicated	

	Screening	Intervention (treatment) Period								Safety Follow-up		Long Term Follow-up	Notes				
Assessment and Procedures	45 Day- to first dose	V1	V2	V3	V4	V5	V6	V7	Until PD	EOT	28 Days (\pm 5 Days) After Last Treatment	12 Weeks (\pm 2 Weeks) After Last Treatment	Every 12 Weeks (\pm 2 Weeks)	D1: All assessments must be performed on day indicated (unless noted in assessment "Notes"). Day 15 through PD: Visits can be performed \pm 3 days. EOT: On day of or within 7 days of decision to discontinue. Follow up: Visits can be performed \pm 2 Weeks.			

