8.3. Evaluation of Anti-Cancer Activity

RECIST version 1.1 guidelines will be used to determine the overall tumor burden at baseline, select target and non-target lesions, and in the disease assessments throughout the duration of the study. The primary measure of response-based efficacy endpoints is according to RECIST v1.1 definition as assessed by the investigator [Eisenhauer, 2009].

- Response assessments will be performed Q8W for the first 6 months and Q12W thereafter, until end of treatment, and at the final study visit (refer to [Table 1](#)).
- If bintrafusp alfa is discontinued without documented progression, then continue imaging Q8W for the first 6 months from first dose of bintrafusp alfa followed by Q12W until documented PD, or the start of any new anti-cancer therapy.
- For post-baseline assessments, a window of [± 3 days] is permitted to allow for flexible scheduling.

Assessments must be performed on a calendar schedule and should not be affected by dose interruptions/delays.

If the last radiographic assessment was 6 weeks or more prior to the participant's withdrawal from study treatment and PD has not been documented, a disease assessment should be obtained at the time of withdrawal from study treatment. See [Table 1](#) for the schedule of assessments of anti-cancer activity.

- All the scans performed during screening need to be repeated at subsequent visits for tumor assessment.
- To ensure comparability between the baseline and subsequent assessments, the same method of assessment and the same technique must be used when assessing response.

Refer to the imaging manual for details on imaging/clinical assessment requirements and submission guidelines.

Tumor responses to treatment will be assigned based on the evaluation of the response of target, non-target, and new lesions according to RECIST v1.1.

Treatment decisions will be made by the treating investigator based on RECIST v1.1. Study intervention should continue until disease progression, unacceptable toxicity, or any criterion for withdrawal from the trial or study intervention occurs (see Section [7](#)). Before stopping the treatment, progressive disease should be confirmed by imaging at least 4 weeks after initial progression according to RECIST v1.1.

See Section 7.1 for more information about continued study intervention after disease progression.

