## 6. GENERAL CONSIDERATIONS

### 6.1. REFERENCE START DATE AND STUDY DAY

Study Day will be calculated from the reference start date and will be used to show start/stop day of assessments and events.

Reference start date is defined as the day of the first administration of study treatment (Day 1 is the day of the first administration of study treatment).

- If the date of the event is on or after the reference date, then:

Study Day = (date of event – reference date) + 1.

- If the date of the event is prior to the reference date, then:

Study Day = (date of event – reference date).

In the situation where the event date is partial or missing, the date will appear partial or missing in the listings, and Study Day, and any corresponding durations will be presented based on the imputations specified in Appendix 2; Partial Date Conventions.

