## 6.3. DERIVED TIMEPOINTS

### 6.3.1. ON-TREATMENT PERIOD

The on-treatment period is defined as the time from first study treatment to the last study treatment date plus 30 days or the earliest date of subsequent anticancer therapy minus 1 day, whichever occurs first, unless otherwise stated.

For participants with treatment ongoing at cut-off date, all data from the first study treatment up to the cut-off date will be considered under the on-treatment period.

Any systemic anticancer therapy, any anticancer surgery and any anticancer radiotherapy as documented in the "Anti-cancer treatment after discontinuation" eCRF page will be considered as subsequent anticancer therapy.

In the case of treatment delay, the definition for on-treatment period remains the same.

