#### 13.1.1. PRIMARY EFFICACY VARIABLE(S) & DERIVATION(S)

The primary efficacy endpoint is the confirmed objective response by the investigator. Overall response rate (ORR) is defined as the percentage (%) of participants with a best overall response (BOR) of PR or CR as assessed by the investigator using RECIST 1.1 out of the total number of participants in the SAF. Tumor response i.e., complete response (CR), partial response (PR), and stable disease (SD), and progressive disease (PD) will be based on the assessments from the investigators' assessment of objective evidence (e.g., radiological scan). Overall responses will be measured in accordance with the RECIST v1.1 (Eisenhauer EA, 2009).

Lesion assessment method and timing, evaluation of disease, disease progression and response criteria will be conducted according to RECIST (version 1.1) as outlined in Section 8.3 of the protocol. If there are multiple scan dates associated with an evaluation, the earliest of the scan dates associated with the evaluation will be used as the date of assessment.

Best overall response (BOR) will be assessed based on the tumor response determined by the investigator at each evaluation timepoint from the first study treatment until the first documented disease progression for RECIST criteria. Only tumor assessments performed before the start of any further anticancer treatment will be considered in the assessment of

Document: [\\quintiles.net\Enterprise\Apps\sasdata\SAS\sas\GSK\GSK4045154\PZAA7715\Biostatistics\Documentation\SAP\GSK\\_213152\\_PZAA7715\\_SAP\\_Final\\_v1.0\\_07SEP2022](\\quintiles.net\Enterprise\Apps\sasdata\SAS\sas\GSK\GSK4045154\PZAA7715\Biostatistics\Documentation\SAP\GSK_213152_PZAA7715_SAP_Final_v1.0_07SEP2022)

Author: PPD Version Number: 1.0

Version Date: 07SEP2022

Template No.: CS\_TP\_BS016 Revision 6

Reference: CS\_WI\_BS005

Effective Date: 02Dec2019

BOR. Clinical deterioration will not be considered as documented disease progression.

Confirmed BOR according to RECIST 1.1 (Eisenhauer EA, 2009) will be assessed according to the following rules:

- CR = at least two determinations of CR at least 4 weeks apart and before progression.
  - Note: It is reasonable to consider CR-NE-CR or CR-PR-CR as CR as long as the second CR is more than 28 days away from the first timepoint.
- PR = at least two determinations of PR at least 4 weeks apart and before progression (and not qualifying for a CR)

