  - Note: It is reasonable to consider PR-NE-PR or PR-SD-PR as PR as long as the second PR is more than 28 days away from the first timepoint.
- SD = at least one SD assessment (or better)  $\geq$  6 weeks after first date of study treatment and before progression (and not qualifying for CR or PR)
- PD = progression  $\leq$  16 weeks after first date of study treatment (and not qualifying for CR, PR or SD)
- NE = all assessments are NE or participant has a missing (or not evaluable) baseline tumor assessment and/or no (or not evaluable) tumor assessments on-treatment, or participant does not complete any of the following response above.

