### 13.1.2. MISSING DATA METHODS FOR PRIMARY EFFICACY VARIABLE(S)

- Participants with no (or not evaluable) post-baseline data are considered as having a non-evaluable response. No missing dates will be imputed for the primary efficacy variable.

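### The NE rule for the primary endpoint rests on on-treatment scans, conflicts with the rest of SAP 13.1, and can overlap with confirmed PR or PD without a tie-break

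*SAP*

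**What the plan says.** SAP 13.1.1 defines confirmed BOR as a list: CR, PR, SD, PD, NE. BOR is taken from the investigator's tumor response "at each evaluation timepoint from the first study treatment until the first" documented progression, leaving out scans made after further anticancer treatment starts. The PR, SD and PD lines each exclude participants who qualify for a better category. The NE line has no such exclusion. It applies when all assessments are NE, or for a missing or non-evaluable "baseline tumor assessment and/or no (or not evaluable) tumor assessments on-treatment, or participant does not complete any of the following response above". These limbs are alternatives. The one at issue is "no (or not evaluable) tumor assessments on-treatment"; the last is a residual limb for anyone who fits none of the categories above.

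SAP 6.3.1 gives the term a meaning: "The on-treatment period is defined as the time from first study treatment to the last study treatment date plus 30 days", or the day before subsequent anticancer therapy if that comes first, unless otherwise stated.

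SAP 13.1.2 works from a different basis: "Participants with no (or not evaluable) post-baseline data are considered as having a non-evaluable response". SAP 7.3 refers missing efficacy data to that section. The NE reasons in 13.1.3 are also framed around post-baseline assessments, and no specific reason covers scans made only after the on-treatment period.

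Protocol 8.3 keeps imaging going off drug: "If bintrafusp alfa is discontinued without documented progression, then continue imaging Q8W for the first 6 months from first dose of bintrafusp alfa", then every 12 weeks until PD or new anticancer therapy.

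**The concern.** Off-treatment scans are planned data, and the BOR window counts them. One limb of the NE line ignores them. Because that limb stands alone and no order of precedence is stated, the same participant can satisfy two categories.

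What is at stake is the numerator of the primary ORR and the split between PD and NE. The denominator is not affected, since it is the whole Safety/Treated set either way. In an open-label, single-arm, investigator-assessed trial, a tie left open in the primary derivation would be settled at the programming stage, with the responses in view. An NE assigned through this limb would fit only the optional not-determined category in 13.1.3.

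**Working it through.** The SAP gives no figure on this point to reproduce. The check is day arithmetic, followed by exact intervals.

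**Inputs**
- SAP 6.1: "Day 1 is the day of the first administration of study treatment". With dosing every 2 weeks (Schedule of Activities, SoA), infusions 2, 3 and 4 fall on D15, D29 and D43.
- SAP 6.3.1: on-treatment end = last dose day + 30 (no new therapy).
- SoA tumor evaluation: D57, then "Q8W up to 6 months., then Q12W", so the next scan is D57 + 56 = D113. Protocol 8.3 allows ± 3 days, so the first scan is D54 to D60.
- Protocol 9.2: N = 25. SAP 13.1.3: two-sided 95% Clopper-Pearson interval.

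**Step 1. Is the first calendar scan on-treatment?**

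| Infusions | Last dose | On-treatment ends | First scan D54–D60 |
|---|---|---|---|
| 1 | D1 | D31 | outside |
| 2 | D15 (D12–D18 with visit window) | D45 (D42–D48) | outside |
| 3 | D29 | D59 | D54–D59 inside, D60 outside |
| 4 | D43 | D73 | inside |

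**Step 2. Does the overlap occur?** PR at D57 and D113 is 113 − 57 = 56 days apart, which exceeds the 4 weeks needed, so it is a confirmed PR. After one or two infusions neither scan is on-treatment. Unless another evaluable scan falls inside the period, the NE limb is met too. In the same way, PD at D57 is 8 weeks after first dose, within the 16-week limit for PD, and also meets NE.

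**Step 3. Could another scan fall inside the period?** Yes.
- The SoA tumor row, as I read its columns, marks scans at end of treatment (EOT; within 7 days of the decision to stop) and at the 28-day visit. That visit is ± 5 days, so 23 to 33 days after last dose: days 23–30 are inside the period and days 31–33 are outside.
- Protocol 8.3 is narrower. It asks for a scan at withdrawal only if the last was at least 6 weeks (42 days) earlier. With the screening scan s days before D1 (s ≤ 28) and the decision on day d, the interval is (d − 1) + s. At d = 14 the maximum is 13 + 28 = 41, so no decision before D15 triggers it. At d = 15 it needs s = 28; at d = 29 it needs s ≥ 14.
- Protocol 7.1 asks for the EOT assessments only where possible.

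**Step 4. Size.** One participant is 1/25 = 4.0 points. The interval runs from the 0.025 quantile of Beta(x, n − x + 1) to the 0.975 quantile of Beta(x + 1, n − x). The responder counts are assumptions:

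| Counted | ORR (95% CI) | One lost | ORR (95% CI) |
|---|---|---|---|
| 3/25 | 12.0% (2.5–31.2) | 2/25 | 8.0% (1.0–26.0) |
| 5/25 | 20.0% (6.8–40.7) | 4/25 | 16.0% (4.5–36.1) |
| 6/25 | 24.0% (9.4–45.1) | 5/25 | 20.0% (6.8–40.7) |

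**The case against.** The other side has real force. The SoA marks scans at EOT and 28 days, and Protocol 8.3 itself refers to that table for assessments through end of treatment, so an early stopper may well have an on-treatment scan. SAP 7.3 points to 13.1.2, which says post-baseline. Section 6.3.1 applies unless otherwise stated, and 13.1.1 states its own BOR window. The safety sections cite 6.3.1 by number and the NE line does not, so on-treatment there could be loose wording for after first treatment. The list runs from best to worst and closes with a residual limb, which suggests that NE was meant to come last. The tumor listing in 13.1 shows imaging dates, last dose and confirmed BOR, so a misassignment would be visible.

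Most of this stands, and it limits the point. It shows what the authors probably meant: count the PR. It does not make the text say so. The on-treatment limb is separate from the residual limb, the defined term is used without qualification, and the exclusion clause carried by PR, SD and PD is missing.

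A reader might infer that anyone who stops after one or two infusions is NE and drops out of the numerator. The documents do not support that. It needs the EOT and 28-day scans to be absent, not evaluable, or later than last dose + 30 days, and then a programmer who prefers NE to an explicit PR rule. Nor do they show that those affected would mainly be stopping for toxicity.

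**Conclusion.** The conflict is real but conditional. As written, SAP 13.1.1 lets one participant be both confirmed PR and NE, or both PD and NE, and its on-treatment limb disagrees with the BOR window and with 13.1.2 and 13.1.3. This requires a stop after one or two infusions (or three, with a late first scan) and no evaluable scan within last dose + 30 days. It also assumes that on-treatment carries its 6.3.1 meaning, and that the SoA columns have been read correctly.

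The number of such participants cannot be found from the documents and may be zero. Each responder lost would cost 4.0 points of ORR at N = 25; an early PD called NE would leave ORR unchanged. The hypothesis text is redacted, so no effect on a decision can be shown. The change is still worth making, because it corrects a stated rule for the primary endpoint at almost no cost.

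**What to change.** In the NE line of SAP 13.1.1:
- replace on-treatment with: post-baseline and before the start of subsequent anticancer therapy;
- keep the other limbs, including the residual one, which captures SD seen only before 6 weeks and a first PD after 16 weeks with no evaluable scan in between (both are listed as NE reasons in 13.1.3);
- state the order CR > PR > SD > PD > NE, so that NE applies only when none of the others is met.

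The cost is one sentence of SAP text and one condition in the BOR program, with no new data.

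Separately, the SoA and Protocol 8.3 differ on when an end-of-treatment scan is required, and the two should be reconciled.

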### 13.1.2. MISSING DATA METHODS FOR PRIMARY EFFICACY VARIABLE(S)

- Participants with no (or not evaluable) post-baseline data are considered as having a non-evaluable response. No missing dates will be imputed for the primary efficacy variable.

### 13.1.3. FINAL ANALYSIS OF PRIMARY EFFICACY VARIABLE(S)

Confirmed BOR will be summarized as the number and percentage of participants with confirmed CR, PR, SD, PD or NE. In addition, the number of participants achieving objective response will be summarized. The corresponding two-sided 95% Confidence Interval (CI) for ORR will be calculated using the Clopper-Pearson (exact) method (Clopper C, 1934) with exact CI for binomial proportion as computed by default by the FREQ procedure using the EXACT option. There will be no adjustments for multiplicity.

Document: [\\quintiles.net\Enterprise\Apps\sasdata\SAS\sas\GSK\GSK4045154\PZAA7715\Biostatistics\Documentation\SAP\GSK\\_213152\\_PZAA7715\\_SAP\\_Final\\_v1.0\\_07SEP2022](\\quintiles.net\Enterprise\Apps\sasdata\SAS\sas\GSK\GSK4045154\PZAA7715\Biostatistics\Documentation\SAP\GSK_213152_PZAA7715_SAP_Final_v1.0_07SEP2022)

Author: PPD Version Number: 1.0

Version Date: 07SEP2022

Template No.: CS\_TP\_BS016 Revision 6

Reference: CS\_WI\_BS005

Effective Date: 02Dec2019

- The following reasons for non-evaluable confirmed best overall response will also be included in the summary:
  - No baseline assessment (if applicable)
  - No post-baseline assessments due to death within 8 weeks after the start of study treatment
  - No post-baseline assessments due to other reasons
  - All post-baseline assessments have overall response “Non-evaluable”
  - New anticancer therapy started before first evaluable post-baseline assessment
  - SD of insufficient duration (<6 weeks after the start of study treatment)
  - No evaluable tumor assessment >16 weeks followed by PD (i.e. tumor assessment of PD was >16 weeks after start of study treatment and there was no evaluable tumor assessment in between)
  - Not determined category may also be added if applicable.

CCI

Document: [\\quintiles.net\Enterprise\Apps\sasdata\SA\SAsas\GSK\GSK4045154\PZAA7715\Biostatistics\Documentation\SAP\GSK\\_213152\\_PZAA7715\\_SAP\\_Final\\_v1.0\\_07SEP2022](\\quintiles.net\Enterprise\Apps\sasdata\SA\SAsas\GSK\GSK4045154\PZAA7715\Biostatistics\Documentation\SAP\GSK_213152_PZAA7715_SAP_Final_v1.0_07SEP2022)

Author: PPD Version Number: 1.0

Version Date: 07SEP2022

Template No.: CS\_TP\_BS016 Revision 6 Reference: CS\_WI\_BS005

Effective Date: 02Dec2019

CCI

Document: [\\quintiles.net\Enterprise\Apps\sasdata\SA\SAsas\GSK\GSK4045154\PZAA7715\Biostatistics\Documentation\SAP\GSK\\_213152\\_PZAA7715\\_SAP\\_Final\\_v1.0\\_07SEP2022](\\quintiles.net\Enterprise\Apps\sasdata\SA\SAsas\GSK\GSK4045154\PZAA7715\Biostatistics\Documentation\SAP\GSK_213152_PZAA7715_SAP_Final_v1.0_07SEP2022)

Author: PPD Version Number: 1.0

[figure not shown]
Version Date: 07SEP2022

Template No.: CS\_TP\_BS016 Revision 6

Reference: CS\_WI\_BS005

Effective Date: 02Dec2019

CCI

Document: [\\quintiles.net\Enterprise\Apps\sasdata\SAStas\GSK\GSK4045154\PZAA7715\Biostatistics\Documentation\SAP\GSK\\_213152\\_PZAA7715\\_SAP\\_Final\\_v1.0\\_07SEP2022](\\quintiles.net\Enterprise\Apps\sasdata\SAStas\GSK\GSK4045154\PZAA7715\Biostatistics\Documentation\SAP\GSK_213152_PZAA7715_SAP_Final_v1.0_07SEP2022)

Author: PPD Version Number: 1.0

Version Date: 07SEP2022

Template No.: CS\_TP\_BS016 Revision 6

Reference: CS\_WI\_BS005

Effective Date: 02Dec2019

CCI

CCI

CCI

[figure not shown]
Document: [\\quintiles.net\Enterprise\Apps\sasdata\SAStas\GSK\GSK4045154\PZAA7715\Biostatistics\Documentation\SAP\GSK\\_213152\\_PZAA7715\\_SAP\\_Final\\_v1.0\\_07SEP2022](\\quintiles.net\Enterprise\Apps\sasdata\SAStas\GSK\GSK4045154\PZAA7715\Biostatistics\Documentation\SAP\GSK_213152_PZAA7715_SAP_Final_v1.0_07SEP2022)

Author: PPD [REDACTED] Version Number: 1.0

Version Date: 07SEP2022

Template No.: CS\_TP\_BS016 Revision 6 Reference: CS\_WI\_BS005

Effective Date: 02Dec2019

Document: [\\quintiles.net\Enterprise\Apps\sasdata\SAS\sas\GSK\GSK4045154\PZAA7715\Biostatistics\Documentation\SAP\GSK\\_213152\\_PZAA7715\\_SAP\\_Final\\_v1.0\\_07SEP2022](\\quintiles.net\Enterprise\Apps\sasdata\SAS\sas\GSK\GSK4045154\PZAA7715\Biostatistics\Documentation\SAP\GSK_213152_PZAA7715_SAP_Final_v1.0_07SEP2022)

Author: PPD [REDACTED] Version Number: 1.0

Version Date: 07SEP2022

Template No.: CS\_TP\_BS016 Revision 6

Reference: CS\_WI\_BS005

Effective Date: 02Dec2019

CCI

CCI

Document: [\\quintiles.net\Enterprise\Apps\sasdata\SA\SAsas\GSK\GSK4045154\PZAA7715\Biostatistics\Documentation\SAP\GSK\\_213152\\_PZAA7715\\_SAP\\_Final\\_v1.0\\_07SEP2022](\\quintiles.net\Enterprise\Apps\sasdata\SA\SAsas\GSK\GSK4045154\PZAA7715\Biostatistics\Documentation\SAP\GSK_213152_PZAA7715_SAP_Final_v1.0_07SEP2022)

Author: PPD

Version Number: 1.0

Version Date: 07SEP2022

Template No.: CS\_TP\_BS016 Revision 6

Reference: CS\_WI\_BS005

Effective Date: 02Dec2019

## Statistical Analysis Plan

Page 35 of 65

CCI

CCI

Document: [\\quintiles.net\Enterprise\Apps\sasdata\SAS\sas\GSK\GSK4045154\PZAA7715\Biostatistics\Documentation\SAP\GSK\\_213152\\_PZAA7715\\_SAP\\_Final\\_v1.0\\_07SEP2022](\\quintiles.net\Enterprise\Apps\sasdata\SAS\sas\GSK\GSK4045154\PZAA7715\Biostatistics\Documentation\SAP\GSK_213152_PZAA7715_SAP_Final_v1.0_07SEP2022)

Author: PPD Version Number: 1.0

Version Date: 07SEP2022

Template No.: CS\_TP\_BS016 Revision 6

Reference: CS\_WI\_BS005

Effective Date: 02Dec2019

CCI

## 14. SAFETY OUTCOMES

All outputs for safety outcomes will be based on the SAF.

There will be no statistical comparisons of safety data, unless otherwise specified within the relevant Section.

### 14.1. ADVERSE EVENTS

Adverse Events (AEs) will be coded using MedDRA V23.0 or later.

Treatment emergent adverse events (TEAEs) are defined as AEs that started or worsened in severity during the on-treatment period, as defined in Section 6.3.1. However, for the first administration of the study treatment, if the AE Start Date is equal to that date, then AEs with the field “Timing related to Bintrafusp alfa” flagged as “Before” on the “Adverse Events Details” form of the eCRF would not be considered a TEAE.

Changes in toxicity grade, seriousness or outcome of AEs are recorded as separate entries in the eCRF with associated end and start dates (start date is equal to or 1 day greater than end date of previous entry). Such entries reporting the same event in such immediately consecutive periods will be considered as one event in the analysis. These events will be kept as separate records in the database and the listing in order to maintain the full detailed history of the events. For tables, the start date of the first treatment emergent record in the sequence is taken as start date of the entire event, similarly the end date of the last event in the

Document: [\\quintiles.net\Enterprise\Apps\sasdata\SAS\sas\GSK\GSK4045154\PZAA7715\Biostatistics\Documentation\SAP\GSK\\_213152\\_PZAA7715\\_SAP\\_Final\\_v1.0\\_07SEP2022](\\quintiles.net\Enterprise\Apps\sasdata\SAS\sas\GSK\GSK4045154\PZAA7715\Biostatistics\Documentation\SAP\GSK_213152_PZAA7715_SAP_Final_v1.0_07SEP2022)

Author: PPD Version Number: 1.0

Version Date: 07SEP2022

Template No.: CS\_TP\_BS016 Revision 6

Reference: CS\_WI\_BS005

Effective Date: 02Dec2019

sequence is taken as end date of the entire event. The overall outcome of the adverse event is the outcome of the last event in the sequence. Duration of the AE and the TEAE flag will be adjusted accordingly in the analysis.

See Appendix 2 for handling of partial dates for AEs. In the case where it is not possible to define an AE as treatment emergent or not, the AE will be classified by the worst-case; i.e. treatment emergent.

An overall summary of number and percentage of participants within each of the following categories will be provided:

- Any TEAE
- Any related TEAE
- Any serious TEAE
- Any related serious TEAE
- Any grade  $\geq 3$  TEAE
- Any related grade  $\geq 3$  TEAE
- Any grade  $\geq 4$  TEAE
- Any related grade  $\geq 4$  TEAE
- Any TEAE Leading to Death
- Any related TEAE Leading to Death
- Any TEAE Leading to study termination
- Any related TEAE Leading to study termination
- TEAEs and related TEAEs of special interest:
  - Infusion-related reactions (IRRs)
  - Immune-related AEs (irAEs)
  - Potential TGF $\beta$ -mediated skin AEs
  - Treatment related anemia
  - Bleeding events
  - Wound healing
  - Secondary Malignancies

In addition, summary tables of the following TEAE categories will be provided by SOC (ordered alphabetically) and PT (ordered alphabetically):

Document: [\\quintiles.net\Enterprise\Apps\sasdata\SAS\sas\GSK\GSK4045154\PZAA7715\Biostatistics\Documentation\SAP\GSK\\_213152\\_PZAA7715\\_SAP\\_Final\\_v1.0\\_07SEP2022](\\quintiles.net\Enterprise\Apps\sasdata\SAS\sas\GSK\GSK4045154\PZAA7715\Biostatistics\Documentation\SAP\GSK_213152_PZAA7715_SAP_Final_v1.0_07SEP2022)

Author: PPD Version Number: 1.0  
Version Date: 07SEP2022

Template No.: CS\_TP\_BS016 Revision 6 Reference: CS\_WI\_BS005

Effective Date: 02Dec2019

- TEAEs
- Related TEAEs
- Serious TEAEs
- Related Serious TEAEs
- TEAEs NCI CTCAE severity grade ( $\geq 3$ )
- Related TEAEs NCI CTCAE severity grade ( $\geq 3$ )
- TEAEs leading to death
- Related TEAEs leading to death
- TEAEs Leading to Permanent Treatment Discontinuation
- Related TEAEs Leading to Permanent Treatment Discontinuation

TEAEs and related TEAEs by worst grade will also be summarized.

All analyses in this Section will be based on TEAEs if not otherwise specified.

A listing will be provided including all AEs (i.e. TEAEs and Non-TEAEs) and will contain the following information: participant identifier, age, sex, race, first and last date of study treatment, preferred term, reported term for the AE, start date, end date, duration of AE (in days), day relative to the first infusion, day relative to the most recent infusion prior to AE onset, relationship to study treatment, toxicity grade, action(s) taken, outcome, seriousness (Y/N), AESI Type (as detailed in section 14.1.6). AEs outside the on-treatment period (prior or after), will be flagged. Additionally, if the AE occurred on the same day as an infusion, a flag of whether the AE was before, during or after the infusion.

In addition a listing summary of Subject Numbers for Individual TEAEs, sorted by SOC and PT in alphabetical order will be presented.

